3.3 Blinding

This study is double-blinded. All MedImmune and contract personnel associated with this study, with the exception of MedImmune Clinical Research and Pharmacy Services (CRPS), including the medical monitor, project management, statistician, site monitors, and data management, will be blinded to the treatment randomization until the study is completed and the database is closed. This includes the medical monitor, project management, statistician, site monitors, and data management. Patients and the study site staff, including the investigators, study nurses, coordinators, pharmacists, and the Clinical Trial Material Manager (CTMM) will remain blinded to the treatment during the study.

Study drug will be supplied to the pharmacy as numbered, blinded kits containing MEDI-545 or placebo vials. The clinical site staff will order study drug from the pharmacy using the site's normal ordering procedures. The CTMM will prepare the study drug from one or more of the appropriate vials (determined by the patient's weight and randomization assignment). Detailed instructions are in the Clinical Trial Material Manual supplied by MedImmune.

A limited number of MedImmune personnel independent of the project team, who will perform and interpret assays such as gene expression signature analyses or PK/PD analyses, will be unblinded during the study. In addition, once the last patient in each dose cohort has completed Study Day 28 and the gene expression analyses are completed, an interim analysis of the gene expression data may be reviewed by senior management for the purpose of making clinical development decisions. Additional interim assessments of safety and clinical activity will be made after the first 2 cohorts complete Study Day 98, after all cohorts complete Study Day 98, and after all cohorts complete Study Day 196. These interim assessments are also for the purpose of making clinical development decisions. Unblinded MedImmune personnel involved in all interim assessments will not be associated with the clinical conduct of the study and will not reveal the treatment assignment of individual patients to any clinical personnel involved in the study. Only changes to the clinical development plan that affect individuals involved in the clinical conduct of the study will be communicated, ie, the actual results of the interim analyses will not be communicated.

In the event the treatment allocation for a patient becomes known to the investigator, the investigator or designated staff must notify MedImmune immediately.

3.4 Study Drug

3.4.1 Study Drug Supplies and Accountability

The sponsor will provide the investigators with adequate quantities of liquid MEDI-545 and placebo. All study drug will be stored at +2°C to +8°C (36°F to 46°F) and must not be frozen.

MEDI-545 (100 mg/mL):

[REDACTED]

PLACEBO:

[REDACTED]

The study CTMM is required to maintain accurate drug accountability records. Upon completion of the study, all study drug accountability records will be returned to the sponsor. All unused study drug must be returned to the vendor designated by the sponsor.

3.4.2 Treatment Regimens

A total of 40 evaluable patients will participate in this study. A total of 32 evaluable patients with positive gene signature will be randomized in a 3:1 ratio to initially receive MEDI-545 (0.3, 1.0, 3.0, or 10.0 mg/kg) or placebo infused over at least 60 minutes every 2 weeks for 12 weeks for a total of 7 doses (Table 1). An additional cohort (Dose Cohort 3B) of 8 evaluable patients with negative gene signature will be randomized in a 3:1 ratio to initially receive MEDI-545 (3.0 mg/kg) or placebo every 2 weeks for 12 weeks for a total of 7 doses, with 6 patients receiving MEDI-545 and 2 patients receiving placebo. In each dose cohort, 6 patients will receive MEDI-545 and 2 patients will receive placebo. Thereafter (2 weeks after the 7th dose), in each of the 5 dose cohorts, patients randomized to MEDI-545 will continue to receive the same dose of MEDI-545 every 2 weeks for an additional 12 weeks (7 doses) and patients randomized to placebo will receive MEDI-545, at the dose specified in the dose cohort they are assigned, every 2 weeks for an additional 12 weeks (7 doses) for a total of 26 weeks (14 doses). MEDI-545 or placebo will be administered IV over at least 60 minutes.

A dose cohort may be expanded by up to 4 additional patients (for a maximum of 20 additional patients in total) if eligible patients are in screening at the time 8 patients have been randomized into the dose cohort.

[REDACTED]

Table 1 Treatment Regimens

Dose Cohort	N	Treatment Period	
		Study Days 0-84	Study Days 98-182
1 ^a	8	MEDI-545: 0.3 mg/kg × 7 doses (N=6)	MEDI-545: 0.3 mg/kg × 7 doses (N=6)
		Placebo × 7 doses (N=2)	MEDI-545: 0.3 mg/kg × 7 doses (N=2)
2 ^a	8	MEDI-545: 1.0 mg/kg × 7 doses (N=6)	MEDI-545: 1.0 mg/kg × 7 doses (N=6)
		Placebo × 7 doses (N=2)	MEDI-545: 1.0 mg/kg × 7 doses (N=2)
3A ^a	8	MEDI-545: 3.0 mg/kg × 7 doses (N=6)	MEDI-545: 3.0 mg/kg × 7 doses (N=6)
		Placebo × 7 doses (N=2)	MEDI-545: 3.0 mg/kg × 7 doses (N=2)
3B ^b	8	MEDI-545: 3.0 mg/kg × 7 doses (N=6)	MEDI-545: 3.0 mg/kg × 7 doses (N=6)
		Placebo × 7 doses (N=2)	MEDI-545: 3.0 mg/kg × 7 doses (N=2)
4 ^a	8	MEDI-545: 10.0 mg/kg × 7 doses (N=6)	MEDI-545: 10.0 mg/kg × 7 doses (N=6)
		Placebo × 7 doses (N=2)	MEDI-545: 10.0 mg/kg × 7 doses (N=2)

a This dose cohort consists of patients who are gene signature positive.

b This dose cohort consists of patients who are gene signature negative.

All patients should continue to receive medications they were taking at the time of consent in unchanged doses during the entire treatment; however, if clinical deterioration occurs and additional treatment is warranted in the opinion of the investigator, the investigator is permitted to add new or increase existing immunosuppressive medications, as long as no prohibited medications are added (see Section 3.4.5). Concurrent immunosuppressive therapy may be tapered and discontinued, according to the investigator’s judgment, during the follow-up period.

3.4.3 Study Drug Ordering and Preparation

Study drug will be sent to the study sites before randomization in a blinded fashion. The dose of study drug for IV administration will be prepared by the CTMM using aseptic techniques. Detailed instructions on study drug preparation can be found in the Clinical Trial Material Manual provided to the study sites.

The volume of study drug infusion is calculated on the basis of the patient’s weight (in kg) measured on Study Day 0 using the following formula:

$$\text{Dose (mL)} = \frac{\text{Pt. Wt (kg)} \times \text{Dose (mg/kg)}}{100 \text{ mg/mL of MEDI-545}}$$

For example: For an 80-kg patient dosed at 10.0 mg/kg MEDI-545, the volume of MEDI-545 required for IV administration would be 8.0 mL.

The MEDI-545 dose for administration must be prepared using aseptic technique. MEDI-545 will be diluted in 0.9% normal saline and the volume will be standardized to 100 mL. The study drug will be administered using an infusion pump over at least 60 minutes as described in Table 2.

Table 2 Summary of Infusion Volume, Duration, and Rate

Dose Cohort	Dose (mg/kg)	Infusion Volume ^a (mL)	Infusion Duration	Maximum Infusion Rate (mL/hr)	Infusion Rate (mg/kg/min) ^b
1	0.3	100	≥ 60 minutes	100	0.005
2	1.0	100	≥ 60 minutes	100	0.017
3A	3.0	100	≥ 60 minutes	100	0.05
3B	3.0	100	≥ 60 minutes	100	0.05
4	10.0	100	≥ 60 minutes	100	0.17

- a. Some study drug will remain in the tubing at the end of the infusion; the remaining study drug should be flushed with 10 mL to 20 mL of normal saline to complete the administration of the entire dose of study medication.
- b. Infusion rate (mg/kg/min) is based on body weight.

The study drug dose will be prepared by the CTMM and administered to patients without blinding.

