5.5 Interim Analyses

Interim analysis of the type I inducible gene expression will be performed after all patients in each dose cohort complete Study Day 28 evaluations.

Interim analyses on the safety and efficacy endpoints will be performed at the following time points in the study:

- After the first 2 cohorts complete the Study Day 98 evaluation;
- When at least 8 patients in Dose Cohort 4 complete the Study Day 98 evaluation; and
- After all cohorts complete Study Day 196 evaluation.

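### Section 3.4.3 of the Protocol says study drug is prepared and given without blinding, which contradicts the double-blind rule in Section 3.3; as a lesser point, Sections 3.3 and 5.5 set different triggers for the second safety and efficacy interim.

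*Protocol*

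**What the plan says.** **Blinding.** Protocol Section 3.3 states "This study is double-blinded". Its list of blinded site roles covers patients, investigators, nurses and coordinators, and ends "pharmacists, and the Clinical Trial Material Manager (CTMM) will remain blinded to the treatment during the study". On supply it says "Study drug will be supplied to the pharmacy as numbered, blinded kits containing MEDI-545 or placebo vials". Section 3.4.3 begins in the same sense: "Study drug will be sent to the study sites before randomization in a blinded fashion". It then gives the dose formula and the infusion table, and ends: "The study drug dose will be prepared by the CTMM and administered to patients without blinding".

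**Second interim.** For the interim assessments of safety and clinical activity, Section 3.3 gives three times: "after the first 2 cohorts complete Study Day 98, after all cohorts complete Study Day 98, and after all cohorts complete Study Day 196". Section 5.5 gives the same first and third times, but its second reads "When at least 8 patients in Dose Cohort 4 complete the Study Day 98 evaluation".

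**The concern.** Section 3.4.3 is where the person preparing the drug looks for instructions. A closing line that removes the blind, with no limit on when or for whom, is an operative instruction in a placebo-controlled trial.

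The outcomes at stake depend on the blind:

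- The primary endpoint summarises adverse events by severity and by relationship to study drug (Section 5.4.1). The investigator assigns both (Sections 4.3 and 4.4).
- Several stopping criteria in Sections 4.7 and 4.8 turn on whether an event is judged related to study drug.
- The Medical Monitor decides on dose escalation from safety information that is meant to be blinded (Section 2.4.1).
- The clinical activity measures are largely ratings.
- With 2 placebo patients per cohort of 8, the concurrent control is small and has little room for biased assessment.

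The interim mismatch is a lesser matter. It leaves unclear when the second look happens and which patients' data it contains.

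**Working it through.** No power or error-rate figure is involved, and Section 5.1 plans no formal tests. The check is a comparison of texts plus simple counts.

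**1. Can the two blinding statements be reconciled?**

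| Point | Section 3.3 | Section 3.4.3, last sentence |
|---|---|---|
| Who | Patients, site staff, pharmacists, CTMM | CTMM (preparing), patients (receiving) |
| Status | Blinded | Not blinded |
| Period | Throughout the study | No limit given |
| Supply | Blinded numbered kits | Section opens with blinded shipment |

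One possible reconciliation is that the sentence is meant only for Days 98 to 182, when everyone receives MEDI-545 (Section 3.4.2, Table 1). The sentence does not say so, and Section 3.3 has no exception for that period: the original assignment stays concealed.

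Appendix K points to the likely origin. In the Version 2.0 to 3.0 changes for Section 3.4.3, the same sentence directly follows one about dosing in an open-label extension. That companion sentence is not in the current Section 3.4.3. The log is used here only to explain the origin; the contradiction lies wholly within the current text.

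**2. Which part of the study is exposed?**

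- Placebo-controlled doses: 7 (Days 0 to 84) of 14 in total.
- Planned allocation: 5 cohorts x 6 = 30 on MEDI-545 and 5 x 2 = 10 on placebo.
- Core set measures (Section 3.6.6.2, Table 6): 6. Physician global, patient global, manual muscle testing, the function questionnaire and extramuscular activity are rated or effort-dependent. Only muscle enzymes are not. That makes 5 of 6.

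**3. Are the two interim triggers the same event?**

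- Section 3.3 requires every cohort to be past Day 98: 5 x 8 = 40 planned patients, or up to 5 x 12 = 60 with the permitted expansion of 4 per cohort.
- Section 5.5 requires 8 patients in Cohort 4, which may hold 12: 8/12 = 67%.
- Cohort 3B is not mentioned in the Section 5.5 trigger, and Section 4.9 has it enrolling in parallel with Cohort 4. Its progress is therefore not tied to that trigger.
- Cohort 3A should not be the difficulty. Cohort 4 opens only after Day 42 data from the first 8 patients in 3A. Expansion patients in 3A were already in screening when the eighth was randomized, and screening lasts at most 28 days, so they are at about Day 42 - 28 = 14 or later when Cohort 4 opens. At least 98 days on, they are at Day 112 or later. This sets aside late replacements and the visit windows.
- Upper bound on patients short of Day 98 when the Section 5.5 trigger is met: without expansion, 8 (all of 3B) of 40, or 20%; with full expansion, 12 in 3B plus 4 in Cohort 4 = 16 of 60, or 27%. Both figures assume that nobody in 3B has reached Day 98, so they are ceilings and not expectations.

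The triggers coincide only if Cohort 3B has finished Day 98 and any extra Cohort 4 patients have too. Numbers beyond the planned 40 are realistic: Section 1.5 reports 51 patients dosed by 02 November 2009, although some may be replacements.

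**The case against.** The strongest reply is that the sentence cannot unblind anyone by itself. It gives the site no treatment code. The IVRS issues a blinded kit number (Section 3.2), drug arrives in blinded kits, and the infusion volume is 100 mL for every dose. Section 1.5 also reports that the data were still blinded after 51 patients had been dosed. All of this stands, and it lowers the practical risk. It does not make the instruction correct. A site could still cite it as permission to relax the blind, and an inspector could not tell which section governs.

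A reader might go further and infer that the blind was lost at all 14 dosing visits. The documents do not support that. Nothing shows that any site acted on the sentence, and for doses 8 to 14 every patient receives MEDI-545, so only the original assignment remains to be concealed.

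A reader might also infer that following Section 5.5 breaches Section 3.3, because codes would be opened while some patients are still on placebo-controlled dosing. Section 3.3 does not forbid this. It allows assay staff independent of the project team to be unblinded during the study. It also allows a gene-expression interim for each cohort at Day 28, which lies inside the controlled period. Its protection is a firewall: unblinded staff stay apart from study conduct, and neither individual assignments nor results are passed on. That firewall covers every interim assessment. Nor does either section require the second interim to be limited to patients who have completed Day 98; that would be a preference.

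**Conclusion.** The concern holds in two parts of unequal weight.

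**Main part.** The last sentence of Section 3.4.3 is wrong as written. It contradicts Section 3.3 and the opening of its own section, and no reading of the current text reconciles them. Its importance lies in the 7 placebo-controlled doses, where severity, causality and 5 of the 6 core measures depend on the blind. The practical risk is reduced by the blinded kits, and no actual unblinding can be inferred. That the sentence is a leftover is an inference from the change log; the contradiction does not depend on it.

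**Lesser part.** The second safety and efficacy interim has two different triggers. Between 0 and 16 patients could be short of Day 98 under the Section 5.5 trigger, depending on the pace of Cohort 3B enrolment and on expansion, neither of which the protocol fixes. With no formal testing planned, there is no effect on type I error. The fault is an inconsistent schedule, not a breach of the blind.

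**What to change.** 1. In Section 3.4.3, delete the last sentence, or replace it with wording such as: the dose is prepared by the blinded CTMM from the assigned numbered kit and administered under the blind described in Section 3.3.
2. Choose one trigger for the second safety and efficacy interim and state it identically in Sections 3.3 and 5.5. Either is workable under the existing firewall.
3. Send sites and pharmacies a short memo pointing out the corrected sentence.

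The cost is a wording amendment and the memo. Sample size, visit schedule and analyses are unchanged.

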3.4.4 Administration of Study Drug

The study drug should be dispensed by the pharmacist or qualified designee and administered as an IV infusion over at least 60 minutes using an infusion pump. Do not ever administer by intravenous push (IVP) or bolus injection. A physician must be present at the site where infusion is given during all administrations of study drug.

Vital signs (blood pressure, heart rate, respiratory rate, and temperature) will be-monitored before, approximately every 15 minutes during infusion, immediately after infusion (within 10 minutes after the infusion has stopped), and approximately every 30 minutes after completion of the infusion until stable, as judged by the investigator. If an anaphylactoid-like infusion reaction or anaphylactic reaction occurs, vital signs will be taken more frequently, as warranted by the severity of the reaction. Blood pressure and heart rate will also be taken prior to discharge from the site on visits in which study drug is administered.

Patients should not be premedicated unless they have had a prior infusion reaction, since the primary objective of this study is to evaluate the safety and tolerability of the study drug. However, if reactions to the IV infusion occur during or after study drug administration, they should be treated appropriately.

Because compatibility of MEDI-545 with IV medications and solutions other than 0.9% Sodium Chloride for Injection, USP, is not known, the study drug solution should not be infused through an IV line in which other solutions or medications are being administered.

Study drug must be administered within 8 hours after preparation. If the dose is not administered within 8 hours, a new dose must be prepared using a new vial as the study drug product contains no bacteriostatic agents.

3.4.4.1 Dose Modification for Toxicity Management: Anaphylaxis and Infusion Reactions

Infusion reactions have been reported with the administration of intravenous gammaglobulin (IVIG) and nearly all approved monoclonal antibodies. Infusion reactions have occurred with the investigational drug MEDI-545. For purposes of this protocol, infusion reactions are defined as anaphylactoid-like AEs related to the infusion of the study drug itself that usually occur within the first 24 hours after infusion, especially within minutes to a few hours, and will be distinguished from true anaphylactic reactions by absence of measurable antibodies against the study drug. Infusion reactions are characterized by a complex of signs and symptoms that include flu-like illness, fever, chills/rigors, nausea, urticaria, headache, bronchospasm, angioedema, hypotension, hypoxia, pulmonary infiltrates, acute respiratory distress syndrome, myocardial infarction, ventricular fibrillation, and cardiogenic shock. For purposes of this protocol, a classification of infusion reactions is given in Table 3, with suggested treatment options. Final treatment is at the discretion of the investigator and should reflect local standard of care.

Table 3 Classification and Suggested Treatments for Infusion Reactions

Severity of Symptoms	Treatment	Study Drug

Mild (Grade 1) Localized cutaneous reactions such as mild pruritus, flushing, rash, dizziness, headache, ≤ 20 point change in systolic BP
	
 • Stop study drug infusion immediately • Evaluate patient, including close monitoring of vital signs • At the discretion of the investigator, treat patient, for example with 
 – Normal saline (~500-1000 mL/hour IV) – Diphenhydramine 50 mg IV – Acetaminophen 500-650 mg 	
 • Option 1: Do not resume infusion; OR, at the discretion of the investigator, resume current infusion under observation and complete study drug infusion at no more than half the planned infusion rate • Option 2: Discontinue further administration of study drug ;OR, at the discretion of the investigator, continue study drug administration and consider slowing infusion rate and pretreating patient 1.5-0.5 hours prior to study drug administration, for example with 
 – Diphenhydramine 50 mg IV – Acetaminophen 500-650 mg

Moderate (Grade 2) Above plus generalized rash or urticaria, palpitations, chest discomfort, shortness of breath, hypo- or hypertension with > 20 point change in systolic BP
	
 • Stop study drug infusion immediately • Evaluate patient, including close monitoring of vital signs • Treat patient, for example with 
 – Normal saline (~500-1000 mL/hour IV) – Diphenhydramine 50 mg IV – Acetaminophen 500-650 mg 	
 • Option 1: Do not resume infusion; OR, at the discretion of the investigator, resume current infusion under observation and complete study drug infusion at no more than half the planned infusion rate • Option 2: Discontinue further administration of study drug; OR, at the discretion of the investigator, continue study drug administration and consider slowing infusion rate and pretreating patient 1.5-0.5 hours prior to study drug administration, for example with 
 – Diphenhydramine 50 mg IV – Acetaminophen 500-650 mg • If moderate event recurs in the same patient, discontinue further study drug administration

Table 3 Classification and Suggested Treatments for Infusion Reactions

Severity of Symptoms	Treatment	Study Drug

Severe (Grade 3) or Above plus fever with rigors, hypo- or hypertension with ≥ 40 point change in systolic BP, wheezing, angioedema, or stridor
 
Life threatening (Grade 4) Defined as a reaction that is life threatening and requires pressor and/or ventilator support or shock associated with acidemia and impairing vital organ function due to tissue hypoperfusion
	
 • Stop study drug infusion immediately • Evaluate patient, including close monitoring of vital signs • Maintain airway, oxygen if available • Treat patient immediately, for example with 
 – Normal saline (~500-1000 mL/hour IV) – Epinephrine for bronchospasm, hypotension unresponsive to IV fluids, or angioedema. Dose and route as per local standard of care, example, epinephrine 1:1000, 0.5-1.0 mL administered SC for mild cases and IM for more severe cases – IV corticosteroids, such as hydrocortisone 100 mg or methylprednisolone 20-40 mg – Diphenhydramine 50 mg IV – Acetaminophen 500-650 mg • Call emergency medical transport for transport to hospital if 
 – Grade 3 wheezing, hypotension or angioedema is unresponsive to single dose of epinephrine – Grade 4 – At the discretion of the investigator 	
 • Do not resume infusion • Discontinue further study drug administration

If an infusion reaction occurs during or after study drug administration, the patient will remain at the study site for a minimum of 2 hours for observation after resolution of symptoms and undergo the following procedures unless transferred to an emergency or hospital facility is deemed warranted for a more severe reaction:

- Clinical evaluation, treatment, and stabilization of patient according to standard medical practice, with suggested approaches outlined above;
- Close monitoring of vital signs, for example every 5 to 10 minutes for Grade 1 or Grade 2 infusion reactions and every 2 to 5 minutes for Grade 3 or Grade 4 infusion reactions until stable;
- Collect serum for assessment of safety biomarkers (including serum levels of mast cell tryptase, cytokines/chemokines, and IgE antibodies) for Grade 1 or higher infusion reactions as soon as possible after the event, at 60 minutes after the event, and at discharge.

